2.3 BENEFIT/RISK ASSESSMENT

The nonclinical toxicological data and the safety data from clinical studies with efpeglenatide to date (with a cut-off date of 22 June 2017) suggest a safety profile consistent with the known AE profile of currently marketed GLP-1 RAs with the exception of potential liver toxicity. The following safety procedures are planned for the clinical study EFC14893:

- Gastrointestinal (GI) disorders such as nausea/vomiting and rarely pancreatitis are the most common AEs to the GLP-1 RAs class. Thus far, no case of pancreatitis has been identified with efpeglenatide. The trend over time for nausea and vomiting events appeared dose related, with an increase after the first injection and generally decreasing thereafter within a period of approximately 2 to 4 weeks. It is anticipated that the planned, gradual dose escalation scheme employed in study EFC14893 will reduce intensity and frequency of GI events, mainly nausea and vomiting.
- Increase in heart rate is a known side-effect of GLP-1 RAs. In study EFC14893, periodic monitoring of vital signs including heart rate and blood pressure will be regularly performed.
- The GLP-1 RA class has a box warning related to risk of thyroid C-cell tumors in the US label, based on findings in rodents. As the relevance for humans is unclear, GLP1-RAs are contraindicated in patients with a personal or family history of medullary thyroid cancer (MTC) or in patients with multiple endocrine neoplasia syndrome Type 2 (MEN-2). In study EFC14893, patients with history of MTC or MEN-2 or with elevated calcitonin levels (≥ 5.9 pmol/L [20 pg/mL]) at screening will not be randomized. Calcitonin will be monitored throughout the study and guidelines for follow-up are provided if this threshold will be reached after randomization.
- Diabetic retinopathy complications have been reported for one of GLP-1 RAs (as of 05 December 2017). No cases have been reported for efpeglenatide in completed Phase 1 and 2 studies. Patients with a recent or planned retinal treatment for retinopathy or maculopathy will be excluded in the current study. Diabetic retinopathy complications will be monitored throughout the study.
- Additional safety monitoring in study EFC14893 includes the collection of AEs, antidrug antibodies (ADA, immunogenicity, [2, 3]), as well as safety laboratory and 12-lead electrocardiogram (ECG).

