8.3 ADVERSE EVENTS AND SERIOUS ADVERSE EVENTS

Adverse event of special interest

An adverse event of special interest (AESI) is an AE (serious or nonserious) of scientific and medical concern specific to the Sponsor's product or program, for which ongoing monitoring and immediate notification by the Investigator to the Sponsor is required. Such events may require further investigation in order to characterize and understand them. The classification of AESI may be changed during the study by protocol amendment (eg, further AE classified as AESI, or AE losing their AESI status).

- Pregnancy of a female participant entered in a study as well as pregnancy occurring in a female partner of a male participant entered in a study with IMP/NIMP (see [Section 8.3.5](#)):
 - In the event of pregnancy in a female participant, IMP should be discontinued.
- Symptomatic overdose (serious or nonserious) with IMP/NIMP:
 - An overdose (accidental or intentional) with the IMP is an event suspected by the Investigator or spontaneously notified by the participant and defined as at least twice the planned dose (eg, two or more injections) if given within 3 days (72 hours),
 - An overdose (accidental or intentional) with the NIMP is an event suspected by the Investigator or spontaneously notified by the participant and defined as at least twice the recommended dose during the planned interval(s),
 - Of note, asymptomatic overdose has to be reported as a standard AE.
- Increase in ALT $>3 \times$ ULN (see Appendix 5 [[Section 10.5](#)]).

The definitions of an AE or SAE can be found in Appendix 3 ([Section 10.3](#)).

Adverse events will be reported by the participant (or, when appropriate, by a caregiver, surrogate, or the participant's legally authorized representative).

The Investigator and any qualified designees are responsible for detecting, documenting, and recording events that meet the definition of an AE or SAE and remain responsible for following up AEs that are serious, considered related to the study intervention or study procedures, or that caused the participant to discontinue the study intervention and/or study (see [Section 7](#)).

Adverse events requiring specific monitoring

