2.4.4 Analyses of safety data

The summary of safety results will be presented by treatment group on the “whole on-treatment period” as defined in [Section 2.1.4](#).

General common rules

All safety analyses will be performed on the safety population as defined in [Section 2.3.2](#), unless otherwise specified, using the following common rules:

- Safety data in participants who do not belong to the safety population (eg, treated but not randomized) will be listed separately

- The potentially clinically significant abnormality (PCSA) values are defined as abnormal values considered medically important by the Sponsor according to predefined criteria/thresholds based on literature review and defined by the Sponsor for clinical laboratory tests, vital signs, and ECG (PCSA version 3 date dated 21 May 2014 effective date 24 May 2014 [[Appendix A](#)])
 - PCSA criteria will determine which participants had at least 1 PCSA during the whole on-treatment period, taking into account all evaluations performed during the whole on-treatment period, including nonscheduled or repeated evaluations. The number of all such participants will be the numerator for the whole on-treatment period PCSA percentage.
 - The treatment-emergent PCSA denominator by group for a given parameter will be based on the number of participants assessed for that given parameter in the whole on-treatment period by treatment group on the safety population.
- The analysis of the safety variables will be descriptive, and no systematic testing is planned.

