21. Congenital and familial/genetic disorders
22. General disorders and administration site conditions
23. Investigations
24. Injury, poisoning, and procedural complications
25. Surgical and medical procedures
26. Social circumstances
27. Product issues

Analysis of all treatment-emergent adverse events

The following TEAE summaries will be generated for the safety population.

- Overview of TEAEs, summarizing number (%) of participants with any
 - TEAE
 - Serious TEAE
 - TEAE leading to death
 - TEAE leading to permanent treatment discontinuation
 - Discontinued per investigator decision
 - Discontinued per participant decision
 - Treatment-related TEAE
 - TEAEs of special interest (AESI)
 - TEAEs requiring specific monitoring (AERSM)
- All TEAEs by primary SOC, HLT, HLT, and PT, showing number (%) of participants with at least 1 TEAE sorted by the SOC internationally agreed order. The other levels (HLT, HLT, PT) will be presented in alphabetical order. This sorting order will be applied to all other tables by SOC, HLT, HLT, and PT, unless otherwise specified.
- Summary of common TEAEs (eg, PTs with incidence $\geq 2\%$ in any treatment group) will be presented by primary SOC and PT

Analysis of all treatment emergent serious adverse event(s)

- All serious TEAEs by primary SOC, HLT, HLT, and PT, showing the number (%) of participants with at least 1 serious TEAE.

Analysis of all treatment-emergent adverse event(s) leading to treatment discontinuation

- All TEAEs leading to treatment discontinuation per investigator decision, by primary SOC, HLT, HLT, and PT, showing the number (%) of participants
- All TEAEs leading to treatment discontinuation per investigator and/or participant decision, by primary SOC, HLT, HLT, and PT, showing the number (%) of participants

Analysis of adverse events of special interest and requiring specific monitoring

Adverse events of special interest (AESI) and adverse events requiring specific monitoring (AERSM) include AE defined in [Section 2.1.4](#) and the criteria of AESI and AERSM are in [Table 1](#).

Table 1 - Criteria for AESI and AERSM

AE Grouping	Criteria
AESI	
Pregnancy	“Pregnancy” or “Partner pregnancy” checked
Symptomatic Overdose	“Overdose” checked and symptomatic (AEOVSYMP) = “Yes”
Increase in ALT >3ULN	“ALT Increase” checked and Yes to the question “Is the event an AESI?” in eCRF form “Adverse Events”
AERSM	
Severe GI event	AE severity = “severe” using CMQ

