Severe hypoglycemia	Any hypoglycemia event which required assistance (from hypoglycemia page)
Pancreatic event	Cases reported in pancreatic specific eCRF page or AE Category = “Pancreatic Neoplasm”
Selected cardiovascular event	Cases reported in the following specific eCRF pages: - ‘Suspected or confirmed MI/Unstable Angina’ - ‘Suspected or confirmed cerebrovascular event’, - ‘Suspected or confirmed heart failure’ led to unplanned hospitalization, led to urgent/unscheduled visit to emergency room or an urgent/unscheduled outpatient heart failure treatment unit, or infusion center, or office/practice visit, not followed by hospitalization, or occurred while patient was hospitalized for another reason - Primary cause of death in eCRF “Death (CV)” as Acute MI, Sudden cardiac death, Heart failure or cardiogenic shock, Stroke, Complication of cardiovascular procedure, Other cardiovascular cause, or Undetermined cause of death
Calcitonin and thyroid C-cell neoplasm	Using Calcitonin increase CMQ Using Medullary thyroid cancer CMQ
Acute renal failure	Using Acute renal failure CMQ
Severe injection site reaction	Intensity = “Severe” + Using Injection site reaction_ CMQ.
Severe allergic reaction	Intensity = “Severe” + CMQs for anaphylactic reaction, angioedema, severe cutaneous adverse reaction, anaphylactic/anaphylactoid shock conditions (under SMQ “Shock”), and hypersensitivity
Severe immune complex disease	Intensity = “Severe” using Immune complex disease CMQ
Diabetic retinopathy complications	Cases reported in eCRF “Diabetic Retinopathy Complementary Form”

The following TEAE summaries will be generated for the safety population:

- All AESI by prespecified grouping and PT, showing number (%) of participants with at least 1 AESI, with PTs sorted by decreasing order in Efpeglenatide 6 mg group.
- All AERSM by prespecified grouping and PT, showing number (%) of participants with at least 1 AERSM, with PTs sorted by decreasing order in Efpeglenatide 6 mg group.

Analysis of adjudicated events

All events of death, selected cardiovascular events (MI, stroke, unstable angina leading to hospitalization, and heart failure leading to hospitalization), any pancreas-related events, and other selected AEs (as defined in the CEC charter) will be reviewed, assessed, and adjudicated by CEC.

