2.4.4.4 Analyses of vital sign variables

The incidence of PCSAs at any time during the whole on-treatment period will be summarized only for heart rate by treatment group irrespective of the Baseline level and/or according to the following Baseline status categories:

- Normal/missing
- Abnormal according to PCSA criterion or criteria

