7 LIST OF APPENDICES

[Appendix A](#) Criteria for Potentially Significant Abnormalities

[Appendix B](#) Schedule of Activities

Appendix A Criteria for Potentially Significant Abnormalities – for Phase 2/3 studies (oncology excepted)

Parameter	PCSA	Comments
Clinical Chemistry		
ALT	By distribution analysis : >3 ULN >5 ULN >10 ULN >20 ULN	Enzymes activities must be expressed in ULN, not in IU/L. Concept paper on DILI – FDA draft Guidance Oct 2007. Internal DILI WG Oct 2008. Categories are cumulative. First row is mandatory. Rows following one mentioning zero can be deleted.
AST	By distribution analysis : >3 ULN >5 ULN >10 ULN >20 ULN	Enzymes activities must be expressed in ULN, not in IU/L. Concept paper on DILI – FDA draft Guidance Oct 2007. Internal DILI WG Oct 2008. Categories are cumulative. First row is mandatory. Rows following one mentioning zero can be deleted.
Alkaline Phosphatase >1.5 ULN		Enzymes activities must be expressed in ULN, not in IU/L. Concept paper on DILI – FDA draft Guidance Oct 2007. Internal DILI WG Oct 2008.
Total Bilirubin	>1.5 ULN >2 ULN	Must be expressed in ULN, not in μ mol/L or mg/L. Categories are cumulative. Concept paper on DILI – FDA draft Guidance Oct 2007. Internal DILI WG Oct 2008.
Conjugated Bilirubin	>35% Total Bilirubin and TBILI>1.5 ULN	Conjugated bilirubin dosed on a case-by-case basis.

Parameter	PCSA	Comments
ALT and Total Bilirubin	ALT>3 ULN and TBILI>2 ULN	Concept paper on DILI – FDA draft Guidance Oct 2007. Internal DILI WG Oct 2008. To be counted within a same treatment phase, whatever the interval between measurements.
CPK	>3 ULN >10 ULN	FDA Feb 2005. Am J Cardiol April 2006. Categories are cumulative. First row is mandatory. Rows following one mentioning zero can be deleted.
CLcr (mL/min)	<15 (end stage renal disease)	FDA draft Guidance 2010
(Estimated creatinine clearance based on the Cokcroft-Gault equation)	≥15 - <30 (severe decrease in GFR) ≥30 - <60 (moderate decrease in GFR) ≥60 - <90 (mild decrease in GFR) ≥90 (normal GFR)	Pharmacokinetics in patients with impaired renal function-study design, data analysis, and impact on dosing and labeling
eGFR (mL/min/1.73m ²)	<15 (end stage renal disease) ≥15 - <30 (severe decrease in GFR) ≥30 - <60 (moderate decrease in GFR) ≥60 - <90 (mild decrease in GFR) ≥90 (normal GFR)	FDA draft Guidance 2010 Pharmacokinetics in patients with impaired renal function-study design, data analysis, and impact on dosing and labeling

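### The SAP counts the ALT >3 x ULN event only from two eCRF answers and schedules no laboratory PCSA table, so ALT rises seen only in central-laboratory data reach no by-arm count

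*SAP*

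**What the plan says.** **The event.** Protocol 8.3 lists an ALT increase above 3 x ULN among the AESIs. Protocol 2.3 describes a safety profile in line with marketed GLP-1 receptor agonists "with the exception of potential liver toxicity".

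**How it is counted.** SAP 2.4.4.1, Table 1, requires the ALT-increase item on the adverse event form to be "checked and Yes to the question" asking whether the event is an AESI. The result feeds this output: "All AESI by prespecified grouping and PT, showing number (%) of participants with at least 1 AESI".

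**Laboratory criteria.** SAP 2.4.4 defines PCSAs for laboratory tests, vital signs and ECG. It gives a numerator rule ("PCSA criteria will determine which participants had at least 1 PCSA during the whole on-treatment period", counting nonscheduled and repeated evaluations) and a denominator rule ("The treatment-emergent PCSA denominator by group for a given parameter will be based on the number of participants assessed"). Appendix A sets ALT categories at >3, >5, >10 and >20 ULN, and a combined category, "ALT>3 ULN and TBILI>2 ULN".

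**What is scheduled.** The analysis subsections of SAP 2.4.4 are adverse events, hypoglycemia, deaths and vital signs, and the SAP table of contents lists the same four. The one PCSA summary among them is in 2.4.4.4, where incidence "will be summarized only for heart rate by treatment group".

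**What was planned and what was dropped.** Protocol Table 7 plans a PCSA incidence summary over the on-treatment period. SAP 1.5 reports no modification to the protocol's statistical section. SAP 1.6 names efficacy, PK and ADA as the analyses affected by early termination.

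**The concern.** The event is defined by a laboratory threshold, but its count depends on an investigator completing two fields correctly. If a rise is never entered as an adverse event, neither the AESI table nor any other adverse event table contains it. The usual safeguard is a by-arm table of laboratory threshold crossings. This SAP defines the ingredients of that table and never asks for it.

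At stake is the by-arm account of the one risk that the protocol singles out. Expected counts are small, so a few uncaptured cases would change what the report shows. By-visit means would not reveal them, because a mean does not say how many participants exceeded 3 x ULN.

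**Working it through.** The point is mainly textual. The plan states no capture rate for ALT events, so there is no figure of its own to reproduce here, and the HbA1c power statement plays no part.

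**Step 1. Follow an ALT value above 3 x ULN through the SAP outputs.**

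| How the rise is recorded | By-arm output under the SAP as written |
|---|---|
| On the AE form, both answers given | AESI table and TEAE tables |
| On the AE form, AESI question not answered Yes | TEAE tables by preferred term only |
| Central laboratory only, scheduled visit | At most a by-visit summary (SAP 2.4); no count above threshold |
| Central laboratory only, unscheduled sample | None |

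The last row follows from three provisions. SAP 2.4 summarizes by scheduled visit, and SAP 2.5.4 uses nominal visits. SAP 2.5.5 admits unscheduled values only for baseline and PCSA. With no laboratory PCSA table, an unscheduled ALT value has no by-arm output. Protocol 10.5.1 refers to an ALT retest within 72 hours, which would usually be such a sample.

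**Step 2. Check whether the omission is declared.** Protocol Table 7 includes PCSA incidence and asks for results in both unit systems, which suits laboratory data. The row boundaries of that table are unclear in the text, so I read the PCSA sentence as covering vital signs, laboratory data and ECG together. SAP 1.5 and 1.6 do not mention laboratory PCSAs. SAP 2.4 says the shortened plan still focuses on safety, among other topics.

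**Step 3. Gauge how many cases could be involved.** Inputs: Phase 2 ALT elevations from protocol 2.3, and 100 participants per arm from SAP 1.3.

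- Efpeglenatide: 12/571 = 0.0210, so 100 x 0.0210 = 2.1 expected per arm and 300 x 0.0210 = 6.3 over three arms.
- Comparators: 3/183 = 0.0164, so 1.6 expected on placebo.

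Let c be the share of laboratory cases given both eCRF answers. The documents do not state c, so the values below are assumptions. Over 300 efpeglenatide participants with p = 12/571, expected missed cases = 300 x p x (1 - c), and P(at least one missed) = 1 - [1 - p(1 - c)]^300.

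| Assumed c | Expected missed | P(at least one missed) |
|---|---|---|
| 90% | 0.6 | 47% |
| 75% | 1.6 | 79% |
| 50% | 3.2 | 96% |

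**Step 4. Effect on the comparison.** If c is the same in every arm, the counts shrink but the expected ratio does not. With full capture it is 2.10/1.64 = 1.28. At c = 75% the expected counts are 1.58 and 1.23 per 100, again a ratio of 1.28. Equal under-capture therefore lowers sparse counts without tilting them.

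**The case against.** The best reply is that the table is already implied. SAP 2.4.4 gives per-parameter PCSA rules that would have little use if heart rate were the only parameter tabulated. Appendix A reads like table layout: its ALT categories are cumulative and the first row, above 3 ULN, is mandatory. Protocol Table 7 planned the summary and nothing withdraws it. Sites must also review every laboratory report and notify AESIs within 24 hours, so capture may be high. A rise reported without the AESI answer still appears among the TEAEs.

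Most of this stands, and it narrows the point to a missing instruction. It does not remove the point, because criteria and computing rules are not a scheduled output. A programmer working from 2.4.4.1 to 2.4.4.4 would produce no ALT threshold table, and nothing in the SAP compares laboratory values with eCRF answers.

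Three stronger readings are tempting and are not supported:

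- **That the SAP limits PCSA tables to heart rate.** That wording sits in the vital-signs subsection and selects among vital signs. It does not exclude laboratory PCSAs.
- **That the count is biased between arms.** Treatment is double-blind and nothing in the documents makes flagging depend on arm.
- **That the AESI should be redefined as any laboratory ALT above 3 x ULN.** The ALT flowchart in protocol 10.5.1 is not shown in the text reviewed, and its surviving footnote ties reporting to a retest. Redefinition could bring unconfirmed values into the AESI.

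**Conclusion.** The point holds as a gap in the SAP. The AESI count rests on two eCRF answers, no analysis subsection schedules a laboratory PCSA table, and the departure from protocol Table 7 is not declared. Followed literally, ALT elevations present only in central-laboratory data reach no by-arm count.

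The size of any loss is unknown. About 2 cases per 100-person arm are expected at the Phase 2 rate, so one missed case would roughly halve an arm's count. That figure carries three cautions: Phase 2 used 3 x ULN or above whereas the AESI uses strictly above; the protocol notes that most Phase 2 cases had confounding factors; and the trial ended early, so arms may be smaller than 100. The capture shares in the working are assumptions. A reader might infer that cases were in fact lost. The documents show only that they could be.

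**What to change.** Add a laboratory subsection to SAP 2.4.4 containing:

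1. One by-arm table of the Appendix A liver categories (ALT >3, >5, >10 and >20 ULN; ALT >3 ULN with total bilirubin >2 ULN), using the numerator and denominator rules already in 2.4.4, so that unscheduled values count.
2. One listing of participants with central-laboratory ALT above 3 x ULN and no matching AESI on the eCRF.

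Leave the AESI definition and its Table 1 rule unchanged. If laboratory PCSA summaries were dropped on purpose, SAP 1.6 should say so and give the reason.

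The cost is one table and one listing from data already collected. The table may include values not confirmed on retest, so a footnote should say that it counts any on-treatment value and need not agree with the AESI count.

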An AE requiring specific monitoring is a serious or nonserious AE of scientific and medical concern specific to the Sponsor's product or program, for which ongoing monitoring may be appropriate. Such events may require further investigation to characterize and understand them. These events should be reported on the AE page and additional information required on the specific eCRF page (where applicable) and will only qualify for expedited reporting when serious (fulfilling SAE criteria).

The AEs requiring specific monitoring for this study are as follows:

- Severe GI events.
- Severe hypoglycemia (see [Section 8.2.5](#)).
- Pancreatic events (including abnormal values of pancreatic enzymes [see Appendix 5, [Section 10.5.2](#)]) will be adjudicated by CEC.
- Major adverse cardiovascular events (MACE; CV death, myocardial infarction, or stroke) and other specific CV events (eg, heart failure leading to hospitalization) will be adjudicated by CEC.
- Calcitonin increase >5.9 pmol/L (20 pg/mL) and thyroid C-cell neoplasm (see Appendix 5, [\[Section 10.5.3\]](#)).
- Acute renal failure (see Appendix 5 [[Section 10.5](#)] for definition).
- Diabetic retinopathy complications; a written report from professional eye care provider will be required.
- Severe injection site reaction.
- Severe allergic reactions.
- Severe immune complex disease.

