10.5.3 Management of participants with increased calcitonin values

During the course of the study, if calcitonin value is found ≥ 20 pg/mL (5.9 pmol/L):

- A retest should be performed by the central laboratory within 7 days.
- The following are to be collected and recorded as soon as possible:
 - Conditions other than C cell disease which may increase calcitonin levels, such as: smoking status, treatment with proton-pump inhibitor (eg, omeprazole), autoimmune thyroid diseases (Hashimoto's thyroiditis or Grave's disease), differentiated thyroid cancer, hypercalcemia, hypergastrinemia, chronic renal insufficiency (not on dialysis), other neuro-endocrine tumors (lung small cell carcinoma, intestinal carcinoid), acute pulmonary inflammatory conditions, or sepsis,
 - Personal and/or familial medical history in relation with thyroid or other endocrine diseases,
 - Specific physical examination (neck, thyroid gland).

If the retest confirms that calcitonin value is ≥ 20 pg/mL (≥ 5.9 pmol/L):

- The event must be reported in the eCRF on the AE form (as final diagnostic if available or as "increased calcitonin"); all appropriate clinical and laboratory documentations should also be reported in the corresponding eCRF pages.
- An ultrasound scan of the thyroid is highly recommended to be performed and the participant may be referred to a Specialist if judged necessary (per clinical practice and local guidelines).

- The participant should continue to be followed according to protocol schedule (including planned calcitonin measurements). The AE form and all other related eCRF pages should be updated with any new information collected during the follow-up.
- If calcitonin value ≥ 50 pg/mL (14.75 pmol/L) is found at any time during follow-up, **the participant should be permanently discontinued from IMP** and referred to a specialist. As far as possible, blood should be collected 1 to 2 weeks after IMP discontinuation and sent to the central laboratory for calcitonin measurement. As per protocol, the participant should be followed according to study procedures up to the scheduled end of the study.

If at any time during follow-up calcitonin value ≥ 20 pg/mL increases by 20% or more between 2 assessments (while remaining below 50 pg/mL), a repeated measurement should be performed earlier than scheduled in the protocol, ie, 1 month later. Once results are available, discussion with Sponsor representative should be initiated without delay for further guidance.

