2.1.4.1 Adverse event observation period

- **Pretreatment AEs** are AEs that developed or worsened or became serious during the pre-treatment period
- **Treatment-emergent AEs (TEAEs)** are AEs that developed or worsened or became serious during the on-treatment period
- **Posttreatment AEs** are AEs that developed or worsened or became serious during the post-treatment period

All AEs (including SAEs, AEs of special interest, and AEs requiring specific monitoring) will be coded to a lower-level term (LLT), preferred term (PT), high-level term (HLT), high-level group term (HLGT), and associated primary system organ class (SOC) using the version of MedDRA currently in effect at the time of database lock.

Adverse events of special interest (AESIs) include the following:

- Pregnancy of a female participant entered in a study as well as pregnancy occurring in a female partner of a male participant entered in a study with IMP/NIMP.
- Symptomatic overdose (serious or nonserious) with IMP/NIMP
- Increase in alanine aminotransferase (ALT) $>3 \times$ upper limit normal (ULN)

Adverse events requiring specific monitoring include the following terms:

- Severe gastrointestinal (GI) events

- Severe hypoglycemia
- Pancreatic events (including abnormal values of pancreatic enzymes, pancreatitis and pancreatic neoplasm)
- Selected cardiovascular events (CV death, MI, stroke, heart failure leading to hospitalization, unstable angina, and transient ischemic attack (TIA))
- Calcitonin increase (≥ 5.9 pmol/L (20 pg/mL)) and thyroid C-cell neoplasm
- Acute renal failure
- Diabetic retinopathy complications
- Severe injection site reaction
- Severe allergic reactions
- Severe immune complex disease

Independent Clinical Endpoint Committee(s) [CEC(s)] will review, assess, and/or adjudicate all events of death, selected CV events, and pancreatic events.

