2.4 STATISTICAL METHODS

In general, descriptive statistics of quantitative efficacy and safety endpoints (result and change from baseline) by scheduled visit will be provided on observed cases (OC), ie, only including participants having a non-missing assessment at a specific visit.

Due to study early termination, the analyses specified in this document focus on demographics, disease characteristics at baseline, exposure, participants disposition, and safety. Primary and secondary efficacy data will be descriptively summarized.

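### Calcitonin rises are counted by arm only through adverse-event terms, and no table counts participants whose measured value reached 20 or 50 pg/mL

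*SAP*

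**What the plan says.** Protocol 2.3 gives the reason for measuring calcitonin: "The GLP-1 RA class has a box warning related to risk of thyroid C-cell tumors in the US label". It goes on: "Calcitonin will be monitored throughout the study and guidelines for follow-up are provided if this threshold will be reached after randomization". SAP 2.1.4.3 lists calcitonin among the central-laboratory safety variables. SAP Appendix B schedules it at screening, baseline, Weeks 12, 30 and 56, and the follow-up visit (Visit 14).

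SAP 2.1.4.1 names the AE requiring specific monitoring (AERSM) as "Calcitonin increase (≥ 5.9 pmol/L (20 pg/mL)) and thyroid C-cell neoplasm". Table 1 in SAP 2.4.4.1 puts this into practice with two AE-term searches, one for raised calcitonin ("Using Calcitonin increase CMQ") and one for medullary thyroid cancer. The output, listed among the summaries of treatment-emergent AEs, is "All AERSM by prespecified grouping and PT, showing number (%) of participants with at least 1 AERSM".

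Protocol 10.5.3 sets out how a measured value becomes an AE. A value of 20 pg/mL or more calls for a central-laboratory retest within 7 days. If the retest confirms it, "The event must be reported in the eCRF on the AE form", as a final diagnosis if there is one and otherwise as increased calcitonin. A second limit, 50 pg/mL (14.75 pmol/L), has its own consequence for study treatment.

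For measured safety data in general, SAP 2.4 promises "descriptive statistics of quantitative efficacy and safety endpoints (result and change from baseline) by scheduled visit" on observed cases.

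**The concern.** The event is defined by a laboratory value but counted by an AE term. Between the two stand a retest, its confirmation, entry of an AE by the site, and a choice of wording that the search must recognise. A value that drops out at any of these steps is not in the by-arm count, although it meets the number in SAP 2.1.4.1.

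Calcitonin of 20 pg/mL or more at screening is an exclusion criterion, so later crossings should be almost all new. The signal to look for is a few participants crossing a limit, more in one arm than another. By-visit averages show that poorly. At stake is whether the report can compare arms on a risk that the protocol names, using measurements taken for that purpose.

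**Working it through.** The plan gives no calcitonin event rate or reporting rate, so there is no stated rate to reproduce. The check is mainly a comparison of rules.

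1. **Limits.** 5.9 / 20 = 0.295 and 14.75 / 50 = 0.295, so the two unit pairs agree. The inequality does not: Protocol 8.3 has "Calcitonin increase >5.9 pmol/L (20 pg/mL) and thyroid C-cell neoplasm", while SAP 2.1.4.1 and Protocol 10.5.3 include the value itself. The two differ only for a result exactly at the limit.

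2. **From measured value to by-arm count** (Protocol 10.5.3, then SAP Table 1).
   - Retested, confirmed, entered as increased calcitonin, on treatment: counted.
   - Not retested, or retested and not confirmed: no AE is required, so normally not counted.
   - Confirmed but not entered by the site: not counted.
   - Confirmed and entered as a diagnosis that neither search covers: not counted in this row.
   - 50 pg/mL or more: counted at most as one more raised-calcitonin event, not distinguished from 20.

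3. **Visit 14.** The visit is 6 weeks ± 1 week after the last dose: 42 − 7 = 35 to 42 + 7 = 49 days. SAP 2.1.4 ends the on-treatment period 30 days after the last injection. Since 35 > 30, an AE with onset at the Visit 14 sample is post-treatment and cannot enter a table of treatment-emergent AEs.

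4. **Whether another rule fills the gap.**
   - SAP Appendix A, the source of the threshold criteria, has rows for ALT, lipase, amylase and creatinine, but none for calcitonin.
   - SAP 2.4.4 has subsections for AEs, hypoglycemia, deaths and vital signs, but none for laboratory data.
   - The general statement in SAP 2.4 gives by-visit results and changes. It gives no count of participants past a limit.
   - SAP 2.4.4.2 does count measured glucose against thresholds, separately from AEs, so the approach already exists in this SAP.

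5. **Illustration only; every input is assumed.**
   - Mean: if 3 of 100 participants in an arm rise from 3 to 25 pg/mL, the arm mean moves by 3 × (25 − 3) / 100 = 0.66 pg/mL and the median hardly at all.
   - Capture: let k participants cross 20 pg/mL, each independently with chance c of being confirmed and entered. The chance that at least one is not counted is 1 − c^k. For k = 2, c = 0.9 it is 1 − 0.81 = 0.19. For k = 2, c = 0.7 it is 1 − 0.49 = 0.51. For k = 5, c = 0.3 it is 1 − 0.00243 = 0.998. A range this wide shows that the size cannot be derived from the documents.

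**The case against.** The strongest reply is that the search row is aimed at the right event. Protocol 10.5.3 makes AE entry mandatory for a confirmed rise and suggests the wording. It also lists conditions other than C-cell disease that raise calcitonin, so leaving unconfirmed single values out of an AE count is defensible. The number in SAP 2.1.4.1 stands in a list of AEs, not in a laboratory derivation. Table 1 treats ALT similarly, through an eCRF entry. A value of 50 pg/mL or more in a participant still on study treatment should also surface among AEs leading to discontinuation. All of this stands, and it limits the gap. It does not close it: ALT has laboratory thresholds in Appendix A and calcitonin has none, and the discontinuation table does not count values.

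The by-visit summaries may also show something. SAP 2.4 does not list their statistics, but where the SAP does list them for continuous data (2.4.1 and 2.4.2.1) they include the maximum. In the illustration, a maximum of 25 at a scheduled visit would reveal that someone crossed. It would not reveal how many did, or whether the same people crossed at successive visits.

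A reader might infer that SAP 2.5.5 bars retests from every calcitonin summary. It says that unscheduled values serve baseline and threshold criteria; it does not say only those. A reader might also infer that calcitonin was singled out. It was not: SAP 1.6 describes a simplified plan after early termination, and laboratory output is not written out for any analyte. That context is fair, but SAP 2.4 keeps safety as a focus, so it does not explain the missing count.

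**Conclusion.** The point holds as a gap in by-arm counting. If the plan is followed as written, no table gives the number of participants per arm with measured calcitonin at or above 20 or 50 pg/mL. A rise first seen at Visit 14 cannot enter the AERSM table, and unconfirmed, non-retested, unentered or differently worded rises are missed as well.

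A reader might go further and infer that rises past the protocol's limits will go unreported. The documents do not support that. Confirmed on-treatment rises must be entered as AEs and should reach the search row, and by-visit summaries may show extreme values.

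The size is unknown; the figures in the illustration rest entirely on assumed crossing and capture rates. The change is worth making because it is cheap and uses data and limits that the trial already has.

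**What to change.** Leave the search row in Table 1 unchanged, as AE reporting. Do not add a laboratory criterion there: the table is presented by preferred term, and a value without an AE has no preferred term.

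Add to SAP 2.4.4 one stand-alone table by arm from central-laboratory data: number (%) of participants by highest post-baseline calcitonin (<20, ≥20 to <50, ≥50 pg/mL), by baseline category. Use scheduled and unscheduled values in the whole on-treatment period, and show post-treatment (Visit 14) values separately. Add a listing of participants with any value of 20 pg/mL or more, with their retest results.

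Separately, the strict inequality in Protocol 8.3 and the inclusive one in Protocol 10.5.3 and SAP 2.1.4.1 must be reconciled, and the table's cut-points aligned with the outcome.

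The cost is SAP wording, one table and a short listing, with no new data and no change to any clinical rule. The drawback is that unconfirmed single elevations will be shown; the retest column identifies them.
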